The IP will be used within the study for continuous measurement of pressure values and their digital documentation with alerts and pressure display off. Potential risks of this equipment are local infections at the suture or in the surgical area. However, pressure sensor catheter and suture are protected by adequate dressing and the sensor will be removed completely about 48 hours after wound closure without reopening the suture.

The IP (without market approval) shall be kept in a locked location with limited and controlled access only for authorized persons at the study site. It will only be used for patients enrolled into the study.

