9.1 Visit Schedule

The timing of study visits and assessments are outlined in Table 1. The term "visit" in the context of study procedures is related to both, clinical visits at the site as well as to documentation forms in the e-CRF.

Assessments and procedures	Baseline	1 month FU ^{1, 3}
Signed informed consent form	х	
Check of inclusion & exclusion criteria	х	
Medical history assessment	х	
Physical examination	х	
Clinical routine laboratory parameters ²	х	
Documentation of concomitant medication	х	
Thyroid surgery ⁵	х	
Generalised Anxiety Disorder questionnaire (GAD-7)	х	x
General Health Questionnaire (EQ-5D-5L)	х	x
Assessment of adverse events ⁴	х	x

Table 1: Study visit schedules and procedures

¹ Time window ± 7 days related to visit schedules as displayed in the e-CRF

² Blood sample not older than 2 weeks at the date of baseline visit

³ By means of patient questionnaires sent to and replied by the patient

⁴ Including provision of external medical documents

⁵ Within 3 months after patient's informed consent

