9.3 Follow-up

The day of index thyroid surgery is day 1 of follow-up on primary and secondary endpoints.

Each patient will be followed until one month after day of index thyroid surgery (\pm 7 days related to visit schedules as displayed in the e-CRF) or until withdrawal of consent (WOC) or death.

9.3.1 Clinical follow-up after 1 month using patient questionnaires

One month after day of index thyroid surgery (± 7 days related to visit schedules as displayed in the e-CRF) or triggered by documentation of withdrawal of consent (WOC), three questionnaires will be sent to the patients by their corresponding study sites together with toll-free envelopes for reply. Patients will be asked to:

- Complete the EQ-5D-5L and the GAD-7 questionnaires
- Document clinical events in a FU questionnaire which are suspicious as AEs.

In case of missing reply after one written reminder by the study site, the patient will be contacted by the study site by phone in order to obtain the required information.

In case a patient reports a clinical event, which is suspicious as SAE, the responsible study site will contact the patient's family doctor, and / or the hospital where the patient was treated, and ask for supporting documents (i.e. hospital discharge letter, diagnostic reports) as applicable. The study site is responsible for completion of the reported event data in the e-CRF.

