Appendix III. Patient questionnaires

Follow-up questionnaire on events

HEDOS-Studie: Patienten-Fragebogen zum Verlauf

Patienten ID: «PatientID», Geschlecht: «Geschlecht», Geburtsjahr: «Geb.Jahr» (Zentrums-ID «CID»)

Sehr geehrte Patientin, sehr geehrter Patient,

seit «Date_baseline» nehmen Sie als Patient(in) der Klinik/Praxis «Institution» («city») an der HEDOS-Studie teil, die Nachblutungen nach Schilddrüsen-Operationen mit einem neuen Diagnosegerät untersucht. Das Auftragsforschungsinstitut CRI in München wurde mit der Durchführung dieser Studie beauftragt.

Zu Beginn Ihrer Studienteilnahme wurden bereits Ihre medizinischen Daten durch Ihre Ärzte für diese Studie dokumentiert. Nun benötigen wir nach ihrer Schilddrüsen-Operation Informationen darüber, wie es Ihnen zur Zeit geht und wie es Ihnen zwischenzeitlich bezüglich Ihrer Gesundheit und auch Ihres Wohlbefindens ergangen ist. So ist es für die Auswertung der Studie auch wichtig zu erfahren, ob Sie seit Ihrer Entlassung nach der Schilddrüsen-Operation beim Arzt oder im Krankenhaus waren.

Wir bitten Sie daher, die folgenden drei Fragebögen vollständig auszufüllen und in dem beigefügten Rückumschlag an CRI in München zu schicken. Sie können den fertigen Rückumschlag ohne Briefmarke in einen Postbriefkasten ihrer Wahl einwerfen, denn das Porto bezahlt CRI.

WICHTIG: Aus Datenschutzgründen enthalten Ihre Fragebögen nur pseudonymisierte Daten, d.h. nur Ihre Patienten-Nummer im Rahmen der HEDOS-Studie sowie Ihr Geschlecht und Ihr Geburtsjahr. CRI kennt Ihren Namen und Ihre Anschrift nicht, daher haben Sie dieses Schreiben und die Fragebögen über Ihr Studienzentrum erhalten. Bitte notieren Sie aus diesem Grund auch keinen Namen auf den Fragebögen oder auf dem Briefumschlag und unterschreiben Sie bitte nicht.

Falls Ihnen Fragen unverständlich vorkommen oder Sie Schwierigkeiten beim Ausfüllen bzw. Fragen zur HEDOS-Studie haben, wenden Sie sich bitte an Ihr Studienzentrum. Die Telefonnummer finden Sie auf Ihrer Patienteninformation.

Wir bedanken uns sehr für Ihre Mithilfe!

Mit freundlichen Grüßen

Ihr HEDOS-Studienteam

.....

н	ED	os-st	udie: P	atienten-Fragebogen zum Verlauf	S	
Pa	tient	ten ID: «	PatientID»	, Geschlecht: «Geschlecht», Geburtsjahr: «Geb.Jahr» (Zentrums-ID «CID»)		
Fra	igeb	ogen v	om Patient	ten ausgefüllt am (Datum):/_/ (Tag / Monat / Jahr)		
1.	 Waren Sie seit Ihrer Entlassung nach der Schilddrüsen-Operation f ür mindestens eine Nacht im Krankenhaus? 					
		Nein				

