		Ja 🗲	Bitte nenn der Klinik	en Sie nachfolgend jeweils Datum, Grund der Krankenhausaufnahme und Na	ne	
	A.	Datum		(Tag / Monat / Jahr)		
		Grund	-			
		Name	der Klinik			
	В.	Datum		(Tag / Monat / Jahr)	-	
		Grund	-			
		Name	der Klinik			
2.	War eine	en Sie s er Arztpro	eit Ihrer En axis?	ntlassung nach der Schilddrüsen-Operation bei einem niedergelassenen Arzt /	in	
		INEIN	Ditte	an Sie aankfelened invesile Datum. Cound and Easthrichtung dae Andre		
	u	Ja 🕇	(z. B. Hau	en Sie nachroigend jeweils Datum, Grund und Fachrichtung des Arztes sarzt, Orthopäde, Chirurg, Neurologe)		
	A.	Datum		(Tag / Monat / Jahr)		
		Grund				
		Fachri	chtung			
-	B.	Datum		(Tag / Monat / Jahr)	-	
		Grund				
		Fachri	chtung			
3.	Wu fes	ırde seit tgestellt'	Ihrer Entla: ?	ssung nach der Schilddrüsen-Operation eine neue chronische Erkrankung		
		Nein				

□ Ja → (bitte beschreiben)

HEDOS

HEDOS-Studie: Patienten-Fragebogen zum Verlauf

Patienten ID: «PatientID», Geschlecht: «Geschlecht», Geburtsjahr: «Geb.Jahr» (Zentrums-ID «CID»)

- Sind seit Ihrer Entlassung irgendwelche Beschwerden oder Krankheitszeichen aufgetreten? (z.B. Infektionen, Kopfschmerzen, Erbrechen etc., unabhängig von der Schilddrüsen-Operation)
 - Nein
 - □ Ja→ Bitte nennen Sie nachfolgend nähere Angaben:

Beschreibung der Beschwerden:	
Beginn:	(Tag / Monat / Jahr)
Intensität:	 Beschwerden sind gut tolerierbar Beschwerden behindern mich in meinem Alltag Ich kann nicht arbeiten oder meinen alltäglichen Aktivitäten nachgehen
Medikamentöse oder medizinische Behandlung dieser Beschwerden:	□ Nein □ Ja, (bitte beschreiben)
Aktueller Zustand:	Beschwerden bestehen nicht mehr Ende am (Tag / Monat / Jahr) Beschwerden dauern heute noch an
Beschreibung der Beschwerden:	
Beginn:	(Tag / Monat / Jahr)
Intensität:	 Beschwerden sind gut tolerierbar Beschwerden behindern mich in meinem Alltag Ich kann nicht arbeiten oder meinen alltäglichen Aktivitäten nachgehen
Medikamentöse oder medizinische Behandlung dieser Beschwerden:	□ Nein □ Ja, (bitte beschreiben)
Aktueller Zustand:	Beschwerden bestehen nicht mehr Ende am (Tag / Monat / Jahr) Beschwerden dauern heute noch an
Beschreibung der Beschwerden:	
Beginn:	(Tag / Monat / Jahr)
Intensität:	 Beschwerden sind gut tolerierbar Beschwerden behindern mich in meinem Alltag Ich kann nicht arbeiten oder meinen alltäglichen Aktivitäten nachgehen
Medikamentöse oder medizinische Behandlung dieser Beschwerden:	□ Nein □ Ja, (bitte beschreiben)

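### The 1-month event questionnaire words its complaints item ambiguously and never asks about the neck wound or probe site, where the protocol's named equipment risk would appear

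*Protocol*

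**What the plan says.** EP3 (section 4.2) is the safety of the device, measured by adverse events within 1 month of surgery. Section 7.1 names the risk to look for: "Potential risks of this equipment are local infections at the suture or in the surgical area". Section 3.3.1 says the same.

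Site staff assess adverse events directly up to hospital discharge (section 9.2.1). The 1-month assessment is then made "By means of patient questionnaires sent to and replied by the patient" (section 9.1, Table 1, footnote 3), and section 9.3.1 asks patients to "Document clinical events in a FU questionnaire which are suspicious as AEs". No visit or wound inspection is scheduled after discharge.

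The event questionnaire in Appendix III has four items:

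1. Overnight hospital stays since discharge, with "Grund der Krankenhausaufnahme" (the reason for admission).
2. Visits to an office-based physician or practice, with "Grund und Fachrichtung des Arztes" (reason and specialty).
3. Any new chronic disease.
4. Complaints: "Sind seit Ihrer Entlassung irgendwelche Beschwerden oder Krankheitszeichen aufgetreten" (have any complaints or signs of illness occurred since discharge), followed by the bracket "z.B. Infektionen, Kopfschmerzen, Erbrechen etc., unabhängig von der Schilddrüsen-Operation".

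None of the four mentions the wound, neck, scar, suture or former probe site.

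**The concern.** The German *unabhängig von* has two senses. One widens the question: report complaints whether or not they are connected with the operation. The other narrows it: report complaints that have nothing to do with the operation. The underlining stresses exactly this word. A patient who takes the narrow sense would leave out a red or discharging neck wound, because it plainly comes from the operation.

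Without an item on the wound or probe site, nothing else on the form corrects that reading for a patient who saw no physician and was not admitted. The study is single-arm (section 5), so no concurrent group would reveal under-reporting. Any omission pushes the recorded rate of local infection downwards. That is the favourable direction for a device whose added individual risk section 3.3.2 already considers negligible.

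**Working it through.** There is no stated figure to reproduce. The check is to follow a local wound problem through each route by which the protocol could learn of it, and to see which routes depend on how the complaints item is read.

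| How the wound problem arises or is handled | Route in the protocol | Depends on the complaints item? |
|---|---|---|
| Before hospital discharge | Site assessment at the baseline visit, 9.2.1 | No |
| Overnight hospital stay after discharge | Item 1, with reason | No |
| Office-based physician or practice | Item 2, with reason and specialty | No |
| Outpatient contact at the study site | Site duty to record any adverse event it learns of until the end of follow-up, 8.1 | No |
| Hospital outpatient or emergency contact elsewhere, no overnight stay | Fits neither item 1 nor item 2 as worded; item 4 only | Yes |
| Managed by the patient alone | Item 4 only | Yes |

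The exposure is therefore the last two rows, and within them only patients who take the narrow sense.

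Next, whether an omission on a returned form would be corrected. Section 9.3.1 provides a written reminder and then a telephone call, but only when the reply is missing. It provides for contacting the family doctor or hospital only when the patient reports something that may be a serious adverse event. A returned form with a mild wound problem left off triggers neither.

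The size can be written down but not filled in. Let r be the true rate of local infection arising after discharge, g the share of those infections falling in the last two rows, and m the share of patients in those rows who omit the event because of the wording. If the other routes work fully:

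- recorded rate = r × (1 − g × m)
- cases lost among the 1,470 planned patients = 1,470 × r × g × m

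The documents give none of r, g or m. The nearest statement, in section 3.3.2, is that previous use of the equipment led to no local infection; no number of patients is given there. What the formula does show is the direction (the recorded rate cannot exceed r through this mechanism) and that the relative loss is g × m. An omission share applied to all infections would be too large, because most routes do not depend on the item.

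**The case against.** The strongest reply is that the harmful reading is the less natural one. The item opens by asking for any complaints at all, infections are its first example, and after such an opening the underlined word most easily widens the scope. That also matches section 8.1, where adverse events count whatever their relation to the device. This stands: the wide sense is probably intended and is the likelier reading. The weakness is that the text permits the other one, and that the prompt for infections gives no location.

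Items 1 and 2 carry no qualifier, and the cover letter says it matters "ob Sie seit Ihrer Entlassung nach der Schilddrüsen-Operation beim Arzt oder im Krankenhaus waren" (whether the patient has been to a doctor or hospital since discharge). This too stands, and it confines the gap to the last two rows of the table.

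The cover letter tells patients to ask the study site if a question is unclear. That helps little, since a patient who takes the narrow sense has no reason to find the question unclear.

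Footnote 4 of Table 1 attaches external medical documents to adverse event assessment in general, so requests need not be confined to serious events. That is fair, but section 9.3.1 spells out the procedure only for suspected serious events, and no request can start from an event the patient did not report.

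Finally, EP3 is a secondary endpoint analysed descriptively (section 12.1.3), with no threshold or test. This stands and limits the consequence.

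**Conclusion.** The point holds as a modest weakness in safety ascertainment. The only scheduled adverse event collection after discharge has an ambiguous qualifier on its one symptom item and no item for the equipment risk the protocol names. The likely loss is confined to wound problems that patients managed alone, or that were treated as hospital outpatients away from the study site, in patients who misread the item. Its size cannot be computed from the documents; its direction is towards a lower infection rate in EP3. EP1 and EP2 are not touched.

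A reader might infer that the form instructs patients to leave out wound infections, that it is the only safety channel after discharge, or that a definite number of infections will be lost. The documents support none of these. The wide sense is the likelier one; section 8.1 adds a continuous recording duty for sites and section 9.3.1 a telephone fallback for non-responders; and any case count would rest wholly on assumed rates.

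The conclusion assumes that items 1 and 2 are answered as worded and that sites record what they see.

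**What to change.** - In Appendix III, replace the bracketed qualifier of the complaints item with wording that has one meaning, for example: *gleichgültig, ob Sie einen Zusammenhang mit der Operation oder dem Messsensor vermuten oder nicht* (no matter whether or not you suspect a connection with the operation or the sensor).
- Add one yes/no item on the neck wound and former probe site, covering redness, swelling, discharge, reopening and any treatment, with the date.
- In section 9.3.1, state that a 'yes' to this item leads the site to request supporting documents by the procedure already described there for suspected serious adverse events.

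The cost is a new questionnaire version with ethics notification and a few extra document requests. The reported infection rate may rise. No sample size or primary analysis changes.

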4.2 Secondary Endpoint Parameters

Secondary endpoint parameters are defined as:

- EP3. Safety of the use of the diagnostic IP by means of adverse events within 1 month following thyroid surgery.
- EP4. Sensitivity and specificity of the IP for detection of clinically relevant hemorrhage within 48 hours following thyroid surgery in a three-level decision system using 10 and 20 mmHg of pressure as cutoffs compared to detection in routine clinical care.
- EP5. Positive and negative predictive values of the IP for detection of clinically relevant hemorrhage within 48 hours following thyroid surgery using the two-level and the three-level decision system compared to detection in routine clinical care.

Clinically relevant hemorrhage and serious adverse events will be adjudicated by an independent Endpoint Review Committee (ERC) according to standardised definitions [7] given in the ERC charter. Outcome death in follow-up will be assessed as equivalent endpoint to clinically relevant hemorrhage.

Parameters relevant for endpoints within the test treatment study (stage 2) are collected within HEDOS study (diagnostic accuracy study, stage 1), too, e.g. clinical symptoms triggering surgical intervention of a suspected post-operative hemorrhage detected in routine clinical care, time to clinical or technical alerts, surgical interventions which did not show post-operative hemorrhage needing intervention.

5. Study Design

In general, the development of a diagnostic test is structured in four phases [1]. In phase I, the functionality and safety of the diagnostic test is examined. In phase II, the diagnostic test is applied to individuals with known disease status to define the cut-off value. Phase III evaluates the diagnostic accuracy based on the pre-defined cut-off value in patients with unknown disease status. Phase IV aims to determine patients' benefit of the test-treatment combination. Hence, the last two phases of the development process are combined. Two single studies are planned to be combined into a phase III/IV seamless design in which a confirmatory phase III diagnostic accuracy study (stage 1) and a subsequent phase IV cluster randomised test treatment study (stage 2) are connected to each other and data from the diagnostic accuracy study will also be used for the randomized test treatment study.

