8.1 Adverse Events (AEs)

Is any untoward medical occurrence, unintended disease or injury, or untoward clinical signs (including abnormal laboratory findings) in subjects, users or other persons, in the context of a clinical investigation whether or not related to the IP. This definition includes events that are anticipated as well as unanticipated events and those occurring in the context of a clinical investigation related to the IP or the procedures involved. For users or other persons, this definition is restricted to events related to IPs.

Any surgery procedure or other intervention irrespective of its relation to the IP or the index thyroid surgery is an AE and has to be documented.

A newly diagnosed concomitant disease is also considered an AE.

All AEs occurring from enrolment until end of follow-up of each study patient will be documented by study site personnel in the e-CRF immediately after study site personnel's awareness of the event, and will subsequently be assessed by the sponsor and reported to authorities involved.

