12.1.3 Analysis of the secondary endpoints

The positive and negative predictive values are reported descriptively with 95%-logit confidence intervals. Their calculation follows from the analysis method chosen for the primary endpoints. To estimate predictive

values with the mixed binary logistic regression model, the true disease status represents the dependent variable. The test results are included as fixed effects and again a random-intercept is estimated for each centre. Positive predictive value is estimated via the calculation of the marginal mean for a test positive result. False-negative rate, which is the counter probability of the negative predictive value, is estimated via the calculation of the marginal mean for a non-diseased individual. Two-sided 95%-logit confidence intervals with pvalues are reported.

Other secondary endpoints, including safety endpoints, will be analysed descriptively.

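### The one-month event questionnaire has no overflow line or total count, so non-serious adverse events after discharge may be under-reported in patients with many events

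*Protocol*

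**What the plan says.** Protocol section 4.2 defines EP3 as "Safety of the use of the diagnostic IP by means of adverse events within 1 month following thyroid surgery". Section 12.1.3 adds: "Other secondary endpoints, including safety endpoints, will be analysed descriptively". Section 8.1 sets the recording duty: "All AEs occurring from enrolment until end of follow-up of each study patient will be documented by study site personnel in the e-CRF".

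For the period after discharge, the footnote to Table 1 in section 9.1 says how the one-month follow-up is done: "By means of patient questionnaires sent to and replied by the patient". Section 9.3.1 gives the patient's task: "Document clinical events in a FU questionnaire which are suspicious as AEs". If no reply comes after one written reminder, the site phones the patient. If the patient reports something that looks like an SAE, the site contacts the family doctor or the treating hospital.

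The event questionnaire in Appendix III has four items:

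- overnight hospital stays: two entries, A and B;
- visits to an office-based doctor: two entries, A and B, each asking for "jeweils Datum, Grund und Fachrichtung des Arztes";
- a newly diagnosed chronic disease: one free-text field;
- any complaints or signs of illness, whether or not related to the operation: after "Bitte nennen Sie nachfolgend nähere Angaben" come three identical blocks, each opening with "Beschreibung der Beschwerden".

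No item asks how many events there were in total, and none says what to do when the space is used up.

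**The concern.** Section 8.1 asks for all adverse events, but the one scheduled instrument after discharge offers a fixed number of places and no route beyond them. The complaints item is deliberately broad, so trivial complaints share three blocks with relevant ones. The visit item does not separate planned aftercare from unplanned visits, so routine post-operative checks can fill both lines.

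A patient who fills every block has returned a form that looks complete. Section 9.3.1 provides a call only for a missing reply and outside enquiries only for a reported suspected SAE, so a non-serious event left off a full form triggers neither. A full form and a truncated form look the same in the data. Any loss is an undercount and falls on the patients with the most events. EP3 is the trial's only safety endpoint, and local infection, the device risk named in sections 3.3.1 and 7.1, can appear after discharge.

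**Working it through.** The plan states no complaint rate and no expected number of adverse events, so there is no figure of its own to reproduce. The check has two parts.

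**1. Which routes bring an event into the record**

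| Event | Route | Depends on space on the form? |
|---|---|---|
| Adverse event up to discharge | Documented by the site (9.2.1) | No |
| SAE | Reported in the e-CRF within 24 hours of the site's awareness (8.4) | No, once the site is aware |
| Event the patient reports to the site unprompted | Entered in the e-CRF on awareness (8.1) | No |
| Non-serious event after discharge, not reported unprompted | Questionnaire (9.3.1, Appendix III) | Yes |

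The e-CRF has no stated limit per patient, but site staff can enter only what they learn of. The weak point is the last row.

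**2. How large the gap could be (illustration)**

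Inputs: three complaint blocks (Appendix III) and 1,470 patients (section 12.2). Assumed: complaints per patient after discharge, X, follow a Poisson distribution with mean m; each block takes one complaint; the patient writes nothing elsewhere.

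- Share of patients with more complaints than blocks: P(X > 3).
- Share of complaints without a block: 1 − E[min(X, 3)] / m, where E[min(X, 3)] = P(X ≥ 1) + P(X ≥ 2) + P(X ≥ 3).

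Example for m = 2: E[min(X, 3)] = 0.8647 + 0.5940 + 0.3233 = 1.7820, so the share without a block is 1 − 1.7820/2 = 0.109. In 1,470 patients that is 1,470 × 2 × 0.109, or about 320 complaints.

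| Assumed mean m | Patients with more than 3 | Of 1,470 patients | Complaints without a block |
|---|---|---|---|
| 0.25 | 0.01% | 0.2 | 0.06% |
| 0.5 | 0.18% | 3 | 0.4% |
| 1 | 1.9% | 28 | 2.3% |
| 2 | 14.3% | 210 | 10.9% |
| 3 | 35.3% | 519 | 22.4% |

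For the two doctor-visit lines, the same formulas with a limit of 2 give 1.4%, 8.0% and 32.3% of patients above two visits at means of 0.5, 1 and 2, and 3.3%, 10.4% and 27.1% of visits without a line. A visit without a line is not in itself a missing adverse event, so these figures show only how soon the lines run out.

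The proportion of patients with at least one event does not change, because the first event always has a block.

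**The case against.** A reader might infer that EP3 is capped per patient. The documents do not support that. EP3 draws on the e-CRF, which has no stated limit and also receives in-hospital events, SAEs and spontaneous reports. The protocol does not define EP3 as a per-patient event count, and it is analysed descriptively in a single arm with no threshold attached.

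Nor does the form strictly hold at most three complaints. The block heading is a plural free-text field, and nothing stops a patient from writing several complaints in one block or adding more in the margin. One event can also appear in several places: an infection can be listed as a complaint (infections are the form's own first example), as the reason for a doctor visit or as the reason for a hospital stay. The form does not ask for date order, so it cannot be said that later events are the ones dropped.

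Other safeguards exist. The cover letter tells patients to contact their study centre if they have difficulty with the form. Section 14.3 provides for ongoing review of e-CRF items with manual queries. Section 11.2 asks investigators to take all acceptable measures to retrieve outcomes.

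All of this stands, and it limits the point. It does not close it. None of these routes asks the patient whether there were further events, and e-CRF review cannot reveal an event that never reached the e-CRF. The calculated shares are complaints without a block of their own, not complaints known to be lost, and at a mean of 0.5 or less they are negligible.

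**Conclusion.** The point holds as a minor one. The only scheduled event collection after discharge has limited printed space, no total count and no overflow instruction, and a returned form prompts no routine call. Non-serious events after discharge may therefore be under-reported in patients with many events, which affects the event counts and event-type tables for EP3. The proportion of patients with at least one event, in-hospital events and SAEs reported separately, and the primary endpoints are unaffected.

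The size cannot be fixed from the documents. With one complaint per block, no extra writing and no capture elsewhere, at most 0.4% to 22.4% of complaints lack a block as the assumed Poisson mean runs from 0.5 to 3. Stronger clustering of complaints within patients would raise these shares at a given mean; writing outside the blocks or capture elsewhere would lower the actual loss. The conclusion also rests on the text of Appendix III as published, in which the layout is partly broken.

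**What to change.** In the Appendix III event questionnaire, add to the complaint, doctor-visit and hospital items (a) a field for the total number since discharge and (b) a line inviting the patient to list further events on an extra sheet. In the doctor-visit item, separate planned aftercare from unplanned visits. In section 9.3.1, extend the existing phone contact to forms on which the stated number exceeds the entries given.

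The total-number field matters most, because it makes a truncated form recognisable. The cost is a revised form with ethics notification, a few extra site calls, and a slightly higher but more complete adverse event count.
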